#### Table 2: Simulations of SAILS under the assumption rosuvastatin is effective

Table 3 gives the results of 10,000 computer simulated clinical trials assuming that rosuvastatin has no effect on mortality. For example, if rosuvastatin has no effect on either VFD or mortality then we would have a 25% chance of stopping on or before the 500 patient look.

 

 Table 3: Simulations of SAILS under the assumption rosuvastatin is not effective (note: futility includes both VFD and Mortality)

Sample size at scheduled interim analysis	Percent of simulations that stop the trial for efficacy
100	0.0%
250	6%
500	19%
750	32%
1000	38%
Total %	96%

#### Subgroup Analyses from data at enrollment:

- 1. AUDIT score analysis
- 2. Shock presence or absence
- 3. Gender, Race, Ethnicity
- 4. Patients naïve to statins vs. those who had been on statins > 48 hours prior to enrollment.
- 5. Pneumonia presence or absence
- 6. Direct vs. Indirect Lung Injury
- 7. Age by quartiles
- 8. CRP level at baseline by quartiles

# 8. Data Collection and Site Monitoring

# 8.1. Data Collection

Research coordinators will collect data and enter it directly into the web-based data entry system managed by the Clinical Coordinating Center or record on paper data forms. Data will be transferred to the Clinical Coordinating Center on a prescribed basis through a web-based data entry program.

# 8.2. Site Monitoring

Site visits will be performed on a regular basis by the Clinical Coordinating Center, to ensure that all regulatory requirements are met and to monitor the quality of the data collected. Records of Institutional Review Board approvals and patients' charts will be examined on a spot check basis to evaluate the accuracy of the data entered into the database.

# 9. Risk Assessment

# 9.1. Risks of Active Study Drug

Potential risks of study drug include hepatic injury, rhabdomyolysis, and interactions with other medications. To limit adverse drug interactions, we have chosen rosuvastatin which has the best drug-drug interaction profile of the currently FDA approved statins. Less than 0.1% of patients receiving rosuvastatin develop a 10 fold increase in CK. Significant rhabdomyolysis or hepatic dysfunction has not been reported in the observational trials of statins in patients with sepsis to date. Rosuvastatin side effect profile is comparable to other statins (Appendix B).

Preliminary data from a study of 60 patients with ALI randomized to simvastatin 80 mg/day versus placebo revealed no differences in AST, ALT or CK values between study groups. Furthermore, the frequency of adverse events, serious adverse events and drug related adverse events were not different (personal communication, [name]).

# 9.2. Risks of Blood Draws

All patients will have blood drawn for research purposes. Most blood will be drawn through indwelling catheters. Risks of drawing blood percutaneously are uncommon and include bleeding and bruising.

# 9.3. Minimization of Risks

Federal regulations at 45 CFR 46.111(a) (1) requires that risks to subjects are minimized by using procedures which are consistent with sound research design. There are several elements of study design in the present protocol that meets this human subject protection requirement.

First, several of the exclusion criteria prohibit participation of patients who might be at increased risk from the effects statins. For example, patients who have intolerances or allergies to statins, active hypothyroidism, and who are taking medications that may unfavorably interact with

statins are excluded. Furthermore, patients with rhabdomyolysis or hepatic injury are excluded as the detection of statin toxicity may be more difficult in such individuals. While these are considered relative contraindications in clinical care, for this trial they will be absolute contraindications.

Second, patients with ALI and ARDS may also have underlying conditions that would benefit from statins as part of usual clinical care, such as ischemic heart disease or hyperlipidemia. We will exclude patients if their attending physician plans to administer statins during the course of ALI for these or any other usual care indications.

Third, there are provisions in the protocol for reduction of the study drug dose for low creatinine clearance by reducing the dose when the serum creatinine is 2.8 mg/dl or greater and for anticipated genetic differences in hepatic drug clearance.

Fourth, levels in the first 60 patients will be evaluated by both the Steering Committee and the DSMB to assure that the achieved levels approximate the targeted range. The Steering Committee recommendation to either maintain or change the study drug dose will be reviewed by the DSMB during the protocol-specified 100 patient safety evaluation.

Finally, we will monitor for adverse effects to liver and muscle by monitoring CK and ALT. We will stop study medications if CK rises to more than 10 times ULN or ALT rises to more than 8 times ULN. Myopathy will be recorded in the case report forms, but study drug will not be stopped unless CK is 10 times ULN.

#### 9.4. Potential Benefits

Most observational studies suggest a mortality benefit from prior or in-patient statin use after hospitalization for serious infections. None of the observational trials have reported significant statin-related toxicity. An animal model of acute lung injury and a human experiment with intravenous LPS demonstrate less lung injury with statins, which may result in shortening the time patients require mechanical ventilation.

#### 9.5. Risks versus Benefits

Several observational and matched cohort studies suggest that statin therapy may reduce mortality in patients with sepsis. No toxicities related to statins were reported despite the critically ill nature of these patients. Preliminary data from a 60 patient RCT of patients with ALI using maximum dose simvastatin (80mg) for up to 14 days also did not reveal increased toxicity when compared to placebo ([name], personal and confidential communication). Specifically, liver function tests and creatinine kinase levels were similar in the simvastatin and placebo groups. Furthermore, a decrease in plateau pressure and improvement in SOFA scores were noted at day 14. Statins are well tolerated in non-septic hospitalized patients with acute stroke, acute coronary syndromes, and in patients undergoing major surgery.

Data from animal studies, human observational and matched case cohort trials, two small clinical studies in normal humans who received intravenous LPS, and one small RCT in patients with

ALI suggest a favorable risk to benefit profile for statins in sepsis-induced ALI and support the conduct of this Phase III trial.

# **10. Human Subjects**

Each study participant or a legally authorized representative must sign and date an informed consent form. Institutional review board approval will be required before any subject is entered into the study.

# 10.1. Selection of Subjects

# 10.1.1. Equitable Selection of Subjects

Federal regulations at 45 CFR 46(a)(3) require the equitable selection of subjects. The ICUs will be screened to determine if any patient meets the inclusion and exclusion criteria. Data that have been collected as part of the routine management of the subject will be reviewed to determine eligibility. No protocol-specific tests or procedures will be performed as part of the screening process. If any subjects meet criteria for study enrollment, then the attending physician will be asked for permission to approach the patient or his/her surrogate for informed consent. Justifications of exclusion criteria are given in Section 4.3. These exclusion criteria neither unjustly exclude classes of individuals from participation in the research nor unjustly include classes of individuals from participation in the research. Hence, the recruitment of subjects conforms to the principle of distributive justice.

# 10.1.2. Justification of Including Vulnerable Subjects

The present research aims to investigate the safety and efficacy of a type of treatment for patients with ALI and ARDS. Due to the nature of these illnesses, the vast majority of these patients will have impaired decision-making capabilities. This study cannot be conducted if enrollment is limited to only those subjects with decision-making capacity. Potential benefits to participation in this study are increased survival and VFDs.

# 10.2. Informed Consent

Federal regulations 45 CFR 46.111(a)(5) require that informed consent will be sought from each prospective subject or the subject's legally authorized representative. The investigator is responsible for ensuring that the patient understands the risks and benefits of participating in the study, and answering any questions the patient may have throughout the study and sharing any new information in a timely manner that may be relevant to the patient's willingness to continue his or her participation in the trial. All study participants or their surrogates will be informed of the objectives of the study and the potential risks. The informed consent document will be used to explain the risks and benefits of study participation to the patient in simple terms before the patient is entered into the study, and to document that the patient is satisfied with his or her understanding of the risks and benefits of participating in the study and desires to participate in the study. The investigator is responsible for ensuring that informed consent is given by each patient or legal representative. This includes obtaining the appropriate signatures and dates on

the informed consent document prior to the performance of any protocol procedures and prior to the administration of study agent.

# 10.3. Continuing Consent

For subjects for whom consent was initially obtained from a surrogate, but who subsequently regains decision-making capacity while in hospital, we will obtain formal consent for continuing participation, inclusive of continuance of data acquisition. The initial consent form signed by the surrogate will reflect that such continuing consent will be obtained when possible.

# **10.4. Identification of Surrogates**

Many of the patients approached for participation in this research protocol will have limitations of decision-making abilities due to their critical illness. Hence, most patients will not be able to provide informed consent. Accordingly, informed consent will be sought from the potential subject's legally authorized representative.

Regarding proxy consent, the existing federal research regulations ('the Common Rule') state at 45 CFR 46.116 that "no investigator may involve a human being as a subject in research...unless the investigator has obtained the legally effective informed consent of the subject or the subject's legally authorized representative"; and defines at 45 CFR 46 102 (c) a legally authorized representative (LAR) as "an individual or judicial or other body authorized under applicable law to consent on behalf of a prospective subject to the subject's participation in the procedures(s) involved in the research." OHRP defined examples of "applicable law" as being state statutes, regulations, case law, or formal opinion of a State Attorney General that addresses the issue of surrogate consent to medical procedures. Such "applicable law" could then be considered as empowering the surrogate to provide consent for subject participation in the research. Interpretation of "applicable law" is therefore state specific and hence, will be left to the discretion of the individual IRBs of the respective clinical centers involved in the ARDSNet.

According to a previous President's Bioethics Committee (National Bioethics Advisory Committee), an investigator should accept as an LAR...a relative or friend of the potential subject who is recognized as an LAR for purposes of clinical decision making under the law of the state where the research takes place. Finally, OHRP has opined in their determination letters that a surrogate could serve as a LAR for research decision making if such an individual is authorized under applicable state law to provide consent for the "procedures" involved in the research study.

# 10.5. Justification of Surrogate Consent

According to the Belmont Report, respect for persons incorporates at least two ethical convictions; first, that individuals should be treated as autonomous agents, and second, that persons with diminished autonomy are entitled to protection. One method that serves to protect subjects is restrictions on the participation of subjects in research that presents more than minimal risks. Commentators and Research Ethics Commission have held the view that it is permissible to include incapable subjects in research that involves more than minimal risk as long as there is the potential for beneficial effects and if the research presents a balance of risks

and expected direct benefits *similar* to that available in the clinical setting. Several U.S. task forces have deemed it is permissible to include incapable subjects in research. For example, the American College of Physicians' document allows surrogates to consent to research involving incapable subjects only "if the net additional risks of participation are not substantially greater than the risks of standard treatment." Finally, the National Bioethics Advisory Committee (NBAC) stated that an IRB may approve a protocol that presents greater than minimal risk but offers the prospect of direct medical benefits to the subject, provided that...the potential subject's LAR gives permission..."

Consistent with the above ethical sensibilities regarding the participation of decisionally incapable subjects in research and the previous assessment of risks and benefits in the previous section, the present trial presents a balance of risks and potential direct benefits that is *similar* to that available in the clinical setting, with the exception of the additional blood draws.

# 10.6. Additional Safeguards for Vulnerable Subjects

The present research will involve subjects who might be vulnerable to coercion or undue influence. As required in 45CFR46.111(b), we recommend that additional safeguards be included to protect the rights and welfare of these subjects. Such safeguards might include, but are not limited to: a) assessment of the potential subject's capacity to provide informed consent, b) requirement for subject's assent, c) the availability of the LAR to monitor the subject's subsequent participation and withdrawal from the study, and d) augmented consent processes. The specific nature of the additional safeguards will be left to the discretion of the individual IRBs.

# 10.7. Confidentiality

Federal regulations at 45 CFR 46 111 (a) (7) requires that when appropriate, there are adequate provisions to protect the privacy of subjects and to maintain the confidentiality of data. To maintain confidentiality, all laboratory specimens, evaluation forms, and reports will be identified only by a coded number. The coded number will be generated at random by a computer, and only the study investigators will have access to the codes. All records will be kept in a locked, password protected computer. All computer entry and networking programs will be done with coded numbers only. All paper case report forms will be maintained in a locked cabinet inside a locked office. Clinical information will not be released without the written permission of the patient, except as necessary for monitoring by the National Heart, Lung, and Blood Institute, the Federal Drug Administration or other authorized Federal Agencies, and the ARDS Clinical Coordinating Center.

# 11. Adverse Event Reporting

Investigators will determine daily if any clinical adverse experiences occur during the period from enrollment through study day 28 or hospital discharge, whichever occurs first. The investigator will evaluate any changes in laboratory values and physical signs and will determine if the change is clinically important and different from what is expected in the course of treatment of patients with ALI. If clinically important and unexpected adverse experiences occur, they will be recorded on the adverse event case report form.

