### **Study Design:**

- 1. Multi-center, prospective, randomized, placebo-controlled clinical trial
- 2. A maximum of 1000 patients will be enrolled
- 3. Participants will be randomized to receive either rosuvastatin or placebo
- 4. Treatment will continue for 28 days, discharge from study hospital or death, whichever comes first.
- 5. All participants will be followed for 7 days following the last dose of study drug for adverse events. Participants will also be followed to the earlier of discharge home on UAB or day 60.

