If used, antacids should be administered no closer than 6 hours before or after administering rosuvastatin to avoid affecting absorption of study drug. The dosage need not be adjusted for concomitant use of ketoconazole, erythromycin, itraconazole, fluconazole, warfarin or digoxin.

**Drug level specimens (venous blood):** The 40 mg loading dose and 20 mg maintenance dose are midrange doses and were selected based on the desire to quickly achieve and maintain plasma levels of rosuvastatin in the range of 10-70 ng/ml (see pharmacokinetic information

below). However, to verify adequate absorption of rosuvastatin, blood for peak and trough plasma rosuvastatin levels will be obtained on day 6 (+/- 2 days) in the first 60 patients and analyzed in the approximately 30 patients randomized to rosuvastatin. Trough levels will be drawn prior to the day 6 (+/- 2 day) dose. Peak levels will be drawn 3-5 hours after the dose.

The target plasma range for modifying lipid metabolism, as measured 3-5 hours after the day 6 (+/- 2 days) dose is expected to be between 10-70 ng/ml of rosuvastatin based on pharmacokinetic studies and reported half life of 10-20 hours. If mean plasma levels are lower than 10 ng/ml then the Steering Committee will consider increasing rosuvastatin loading and/or maintenance doses. If mean plasma levels are greater than 70 ng/ml, then the decision to modify the current dose will be based primarily on safety and early indications of efficacy. A formal recommendation regarding dose adjustments for high drug levels is not possible as the relationship, if any, of plasma levels to either the pleiotropic effects or the toxicities of statins is unknown. Dose changes will be recommended by the investigators and independently reviewed by the DSMB who will have unblinded access to the drug levels, adverse events, clinical and laboratory findings, and study outcomes.

**Completion of study drug administration:** Study drug administration will be stopped when one of the following conditions is met, whichever comes first:

- 1. 28 days after randomization or three days after ICU discharge (whichever occurs first)
- 2. Discharge from study hospital
- 3. Death

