# 3.5. Focused Safety Analysis:

The incidence of elevations in CK > 10 times ULN, AST > 8 times ULN, and ALT > 8 times ULN measured on days 0, 1, 3, 6, 14, and 21 (additional CK on day 10).

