# 5.3. Completion of Study Drug Administration

Patients will be considered to have completed the study drug administration portion of the study and the study drug will be stopped when one of the following conditions is met, whichever comes first:

- 1. 28 days after randomization or 3 days after ICU discharge (whichever comes first)
- 2. Discharge from study hospital
- 3. Death

Note: If patient is readmitted to the ICU while still on study drug before day 28, study drug should continue until three days after the next ICU discharge or day 28, whichever comes first. If the study drug administration has been completed and the patient is subsequently readmitted to the ICU, no further study drug should be administered.

The optimal duration of statin therapy for sepsis-induced ALI is unknown. The decision to examine a relatively long duration of therapy of up to 28 days was based on observational trials showing benefit with little or no toxicity when statins were continued throughout the ICU and hospital course. Furthermore, statin use in observational studies was of long duration prior to admission. The relative ease of once daily oral study drug administration was also considered in determining the duration of therapy.

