# 6.3. Assessments after Enrollment

The following data will provide the basis for assessing protocol compliance and safety as well as between-group differences in several efficacy variables. Data for each of the variables will be recorded on the days shown in the Time-Events schedule (Appendix F) or until death, discharge from the intensive care unit, or unassisted ventilation for 48 hours.

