#### **Reference Measurements**

The following parameters will be measured and recorded using values closest in time to 8:00 A.M. on the days specified in the Time-Events schedule (Appendix F). The following conditions will be ensured prior to measurements: no endobronchial suctioning for 10 minutes; no invasive procedures or ventilator changes for 30 minutes. All vascular pressures will be zero-referenced to the mid-axillary line with the patient supine.

- 1) If receiving assisted ventilation record daily up to day 7:
  - a) Tidal volume, FiO2, PEEP, inspiratory plateau pressure, and mean airway pressures
  - b) Pressure during inspiration if on a pressure targeted mode (PSV, PCV, etc).
  - c) Arterial PaO2, PaCO2, pH and SpO2
- 2) CK, AST, ALT as in schedule of events (Appendix F)
- 3) Fluid intake and output
- 4) Vital signs: Heart rate, systolic and diastolic blood pressure, body temperature, CVP
- 5) Modified Brussels Score data days 0-14:
  - a) Vasopressor use (Y/N), worst systolic BP, creatinine, bilirubin, and platelet count for the day. The date and value of the highest creatinine between days 15-28
- 6) CAM-ICU delirium screening assessment and RASS or RIKER sedation score through ICU discharge or study day 28 at select hospitals
- 7) Presence of myopathy
  - 8) Frontal Chest Radiograph Lung Injury Score
- 9) Occurrences of VTE, myocardial infarction, bowel ischemia, ischemic stroke and arrhythmias requiring treatment
- 10) Methylprednisolone equivalents greater than 20 mg
- 11) Daptomycin administration
- 12) Concomitant medications: niacin, fenofibrate, cyclosporine, gemfibrozil, lopinavir, ritonavir, or oral contraceptives. (Yes/No each day). The type and dose of statins prescribed as part of usual care if the study drug is withdrawn by the treating physician during the treatment period or prescribed after the treatment period will be recorded.
- a) Study drug/placebo will be stopped should one of these medications be started.
   13) Blood and urine for cytokines, mediators, and markers of inflammation. Plasma obtained from two, 10 ml EDTA anti-coagulated blood samples will be divided immediately after centrifugation into 4 equal 2 ml aliquots and frozen at -70°C. Urine obtained from the patients will be collected in an 8 ml sample tube and divided into 4 equal aliquots in specified tubes and frozen at -70°C. Specimens will be collected on days 3 and 6.
- 14) Plasma CRP levels on days 6 and 14

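### Safety-observation stop points conflict: Section 11 drops the 7-day post-dose adverse-event follow-up stated in Part I, and Section 6.3 leaves unclear how long CK, AST and ALT are collected

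*Protocol*

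**What the plan says.** **Adverse-event follow-up.** Part I, Study Design item 5: "All participants will be followed for 7 days following the last dose of study drug for adverse events". Section 11 instead has investigators look for events daily "from enrollment through study day 28 or hospital discharge, whichever occurs first", with no reference to the last dose. Appendix F has a third rule, for myopathy and for MI, VTE, ischemic stroke and bowel ischemia: collection until 72 hours after drug is stopped.

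**CK, AST and ALT.** Section 3.5 defines the focused safety analysis on values "measured on days 0, 1, 3, 6, 14, and 21 (additional CK on day 10"). Section 6.3 opens by saying that its variables are recorded on the Appendix F days "or until death, discharge from the intensive care unit, or unassisted ventilation for 48 hours". Item 2 of the list that follows is "CK, AST, ALT as in schedule of events (Appendix F"). Appendix F marks these tests as required up to day 21. Its 48-hour unassisted-breathing mark is on ventilator parameters and vital signs, and its ICU-discharge marks are on the Brussels score and arrhythmias. The CK, ALT and AST rows carry neither.

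**End of dosing.** Part I, Study Design item 4: "Treatment will continue for 28 days, discharge from study hospital or death, whichever comes first". The Part I paragraph on completion of study drug gives "28 days after randomization or three days after ICU discharge (whichever occurs first"), and Section 5.3 gives "28 days after randomization or 3 days after ICU discharge (whichever comes first"). Both also stop at study-hospital discharge or death. Reaching unassisted breathing does not stop the drug.

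**The concern.** Sites need one answer to two questions: until when do we look for adverse events, and until when do we draw CK, AST and ALT? The protocol gives more than one answer to each.

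For adverse events, a site that follows Section 11 may collect nothing after the last dose, while a site that follows Part I collects another week. Events not collected cannot be recovered at analysis.

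For the laboratory tests, the drug-stopping thresholds in Section 5.4 and the focused safety analysis in Section 3.5 both depend on these values, and Section 9.3 cites CK and ALT monitoring as a protection for participants. If collection ended at extubation plus 48 hours or at ICU discharge, the missing values would follow ventilator and ICU status. Ventilator-free and ICU-free days are secondary endpoints that the drug is hoped to improve. If it did improve them, the active arm would have fewer draws and fewer chances to show an elevation, so the safety comparison would lean towards the drug.

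**Working it through.** The plan gives no figure to reproduce; the check is day arithmetic. The patient timelines are illustrative assumptions, with no ICU readmission and no early stop under Section 5.4. I take hospital discharge in Section 11 to mean discharge from the study hospital.

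**Step 1. Adverse-event window.** Let I be the day of ICU discharge and H the day of hospital discharge.

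- Last dose (Section 5.3): L = min(28, I + 3, H)
- End of follow-up, Part I: L + 7
- End of follow-up, Section 11: E = min(28, H)

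| I | H | Last dose L | Part I end | Section 11 end | Post-dose days covered, of 7 |
|---|---|---|---|---|---|
| 40 | 60 | 28 | 35 | 28 | 0 |
| 26 | 35 | 28 | 35 | 28 | 0 |
| 12 | 12 | 12 | 19 | 12 | 0 |
| 7 | 14 | 10 | 17 | 14 | 4 |
| 20 | 30 | 23 | 30 | 28 | 5 |
| 9 | 20 | 12 | 19 | 20 | 7 |

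E is never earlier than L, because L is a minimum over the same two terms plus one more. Section 11 therefore never closes before dosing does. Coverage is zero whenever I + 3 is at or beyond min(28, H), that is, for patients dosed to day 28 or discharged from hospital on drug. It is partial or complete for patients who stop drug 3 days after ICU discharge and stay in hospital.

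**Step 2. CK, AST and ALT under the restrictive reading of 6.3.** Recording would stop at the earlier of ICU discharge and completion of 48 hours of unassisted breathing.

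- 48 hours completed on day 5, ICU discharge on day 7, still in hospital on day 10: recording stops on min(5, 7) = day 5 and dosing on 7 + 3 = day 10. The required draws falling between are the day 6 CK/ALT/AST set and the day 10 CK.
- Unassisted breathing from day 8, ICU discharge on day 20, hospital discharge on day 30: recording stops on min(8 + 2, 20) = day 10 and dosing on min(28, 23, 30) = day 23. The day 14 and day 21 sets fall between.
- If ICU discharge is itself the binding stop, the gap to the last dose is at most 3 days.

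**Step 3. CK, AST and ALT under Appendix F alone.** The last scheduled test is day 21 and dosing can run to day 28: 28 − 21 = 7 days with no scheduled test. With the two-day window that Appendix F gives CK and ALT, the last draw falls on days 19 to 23, so the gap is 28 − 23 = 5 to 28 − 19 = 9 days.

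**Step 4. End of dosing.** With ICU discharge on day 9 and hospital discharge on day 20, Part I item 4 gives min(28, 20) = day 20. The Part I completion rule and Section 5.3 give min(28, 9 + 3, 20) = day 12.

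**The case against.** Several stronger readings are tempting, and the documents do not support them.

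- *Adverse-event observation under Section 11 ends while patients are still being dosed.* It does not, by Step 1. The loss is in the post-dose week only.
- *Section 6.3 plainly stops the laboratory tests.* The wording is ambiguous, and the context points the other way: the item on CK, AST and ALT refers to Appendix F, whose rows for these tests carry no such cut-off. Other items in the same list, such as day 14 CRP and the highest creatinine in days 15 to 28, also make little sense under a hard stop. The contradiction on the page stands, but I would not assume that sites would follow the restrictive reading.
- *Every dosed day after the 6.3 stop is an unmonitored day.* In the first example in Step 2 that would be 10 − 5 = 5 days, or 28 − 5 = 23 if item 4 governed dosing. These tests are not required daily, so such counts include days on which nothing was due. The loss should be counted in scheduled draws. Even the day 6 CK and ALT could be taken on day 4 or 5 within the two-day window.
- *Part I and Part II test different regimens.* The Part I completion rule agrees with Section 5.3. Item 4 is an outline statement that leaves out one stopping condition.
- *Late events would go unrecorded altogether.* The 72-hour collection in Appendix F remains, and the 24-hour reporting duty for serious, unexpected, study-related events states no day-28 or discharge limit.

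What stands against these points is that none of them restores the 7-day follow-up for events in general, and Appendix G refers to a study period without defining it.

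**Conclusion.** The safety stop points conflict and need reconciling. The firmest part is the adverse-event window: two plain statements disagree, and patients dosed to day 28 or discharged on drug have 0 of the 7 stated post-dose days under Section 11. The laboratory part is conditional. If the opening of Section 6.3 governs, scheduled draws are lost in patients still on drug, in a pattern linked to extubation and ICU discharge. If Appendix F governs, what remains is the interval from day 21 to day 28 (5 to 9 days for CK and ALT with the sampling window). The dosing-end mismatch is an omission in Part I item 4.

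The day counts rest on assumed timelines. The documents do not say what share of patients would be affected, so the effect on the safety comparison cannot be sized. Severity is moderate: safety ascertainment is affected, but the primary endpoint and its analysis are not.

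**What to change.** 1. **Adverse-event window.** Align Section 11 with the 7-day post-dose follow-up already in Part I, or otherwise state one identical window in both places.
2. **Section 6.3.** State that the ICU-discharge and 48-hour cut-offs apply only to the variables so marked in Appendix F, and that CK, AST and ALT are collected on the Appendix F days.
3. **For the sponsor to reconcile.** Part I item 4 with the Part I completion rule and Section 5.3; and the last scheduled test on day 21 with dosing that can run to day 28. This review takes no position on treatment duration or on any clinical rule.

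Cost: amendment wording, a short contact after discharge for patients who leave hospital before the window closes (already implied by Part I), and slightly more safety data after ICU discharge.
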